3.7 Interaction between the estrogen receptor and PI3K/Akt/mTOR pathway

The estrogen receptor and PI3K/Akt/mTOR pathways cross-communicate, and the former is capable of activating the latter (Figure 3) [114]. In breast cancer, selective downregulation of the PI3K/Akt/mTOR pathway is one of several mechanisms by which anti-estrogens exert their anti-mitogenic effects [115]. However, this pathway may eventually upregulate in response to prolonged estrogen-deprivation, allowing the cells to “escape” suppression and acquire resistance to anti-estrogens [116,117]. *In vitro* studies have demonstrated that breast cancer cells refractory to tamoxifen and aromatase inhibitors can be resensitized to these agents with the addition of the mTOR inhibitors everolimus and rapamycin [118,119]. This phenomenon has been reproduced in the clinical setting. In a phase I trial conducted in metastatic breast cancer patients with stable or progressive disease on letrozole, the addition of everolimus produced one complete response lasting 22 months, and 50% of patients had stable disease (lasting \geq 6 months in a third of patients) [120]. Similarly, combination therapy with temsirolimus and letrozole has shown activity in heavily pretreated metastatic breast cancer patients [121]. Furthermore, a phase II study in treatment-naïve patients with operable breast cancer reported a significantly higher clinical response rate with neoadjuvant letrozole and everolimus compared to letrozole alone [122]. These findings support the use of dual aromatase and mTOR inhibition given either in sequence, or in combination upfront.

Figure 3: Cross-communication between the estrogen receptor and PI3K/Akt/mTOR pathway (AI = aromatase inhibitor, ER = estrogen receptor, E2 = estrogen) [114].

3.8 Dosing and safety of dual aromatase and mTOR inhibition in the clinical setting

Dual aromatase and mTOR inhibition was evaluated in a phase I trial of letrozole at the standard dose of 2.5 mg PO QD, with two different dose levels of everolimus at 5 mg PO QD or 10 mg PO QD [120]. Safety and pharmacokinetic studies revealed the combination to be safe, with no major interactions at either dose level of everolimus. Only one dose-limiting toxicity, grade 3 thrombocytopenia, occurred in the everolimus 10 mg PO QD cohort. A randomized phase II neoadjuvant breast cancer trial of letrozole 2.5 mg PO QD plus everolimus 10mg PO QD or placebo also reported an acceptable toxicity profile for the combination, with grade 3/4 toxicities occurring in $\leq 5\%$ of patients receiving everolimus [122]. This included three patients who developed pneumonitis which resolved within two weeks of everolimus discontinuation.

EVOLVE-1 is a phase III trial of everolimus at 7.5 mg PO QD versus best supportive care in advanced typical HCC following failure/intolerance of sorafenib (www.clinicaltrials.gov, NCT01035229). The reduced dose of 7.5 mg PO QD was chosen given concerns about pneumonitis at the 10 mg PO QD dose, particularly in a patient population with abnormal hepatic drug clearance. Although most patients with FLL-HCC have normal hepatic parenchyma, hepatic reserve may be somewhat impaired by the presence of tumor. Thus, for the purpose of this trial, everolimus 7.5 mg PO QD will be administered.

4.1 OVERVIEW OF STUDY DESIGN/INTERVENTION

4.2 Design

This is a multi-institutional randomized three arms phase II clinical trial, consisting of two parts. In Part 1 of this study, patients with advanced (recurrent or metastatic), unresectable FLL-HCC will be randomized to one of three arms: Arm A (everolimus 7.5 mg PO QD); Arm B (EDT with letrozole 2.5 mg PO QD + leuprolide 7.5 mg IM monthly); or Arm C (everolimus + EDT). Upon disease progression, patients in Arm A or Arm B may proceed to Part 2 of the study in which they will receive combination therapy with both everolimus and EDT. Please refer to Figure 1 (page 4) for a schematic of the study design.

4.3 Intervention

Patients randomized to Arm A will receive everolimus 7.5 mg PO QD.

Patients randomized to Arm B (EDT) will receive leuprolide and letrozole to provide central and peripheral suppression of estrogen production, respectively.

- Leuprolide will be administered as a monthly depot injection of 7.5 mg IM.
- Bloodwork will be drawn 1 week after the first injection of leuprolide to measure serum estradiol levels in females and serum testosterone levels in males.
- Letrozole 2.5 mg PO QD will be started 1 week after leuprolide is given if serum testosterone and estradiol levels are found to be within the castration range. Otherwise, initiation of letrozole will be delayed until week 4, coinciding with the second dose of leuprolide.

Patients randomized to Arm C (EDT + everolimus) will receive everolimus, leuprolide and letrozole at the same doses and schedule as outlined for Arms A and B.

5.1 THERAPEUTIC/DIAGNOSTIC AGENTS

5.2 Everolimus

- Definition: everolimus is a rapamycin analog that inhibits the mammalian target of rapamycin (mTOR) serine-threonine kinase. everolimus binds intracellular FK506 binding protein-12 (FKBP-12) which subsequently complexes with mTOR, inhibiting its downstream effectors such as S6 kinase and 4E-BP1 [123-126]. everolimus is also a macrolide immunosuppressant that blocks mitogenic signaling in T cells [127]. everolimus has anti-proliferative and anti-angiogenic effects through its suppression of vascular endothelial growth factor (VEGF) and hypoxia inducible factor 1- α (HIF1- α) [124]. It is rapidly absorbed, reaching peak serum concentrations within 1.5-2 hours and has a half-life of about 30 hours [125,127]. everolimus undergoes extensive hepatic metabolism by CYP3A4 and is excreted fecally and, to a lesser extent, in the urine [128].
- For patients age 12-18, everolimus dose is reported as 5 mg/m² [129,130]. Patients with a body surface area (BSA) < 1.5 m² will receive everolimus 5 mg PO QD. Patients with a BSA \geq 1.5 m² will receive everolimus 7.5 mg PO QD.

- Supply: Everolimus is manufactured by Novartis Pharmaceuticals. As an anti-neoplastic agent, everolimus is supplied as 2.5 mg or 5 mg oral tablets. Everolimus is supplied by Novartis for this study.
- Storage: Everolimus should be stored at an ambient temperature of 25 °C (77 °F) with brief temperature excursions ranging from 15 °C-30 °C (59 °F-86 °F) permitted. The drug should be stored in its original packaging, and exposure to light and moisture should be avoided [131].
- Administration: Everolimus is administered orally, once daily, with or without meals.
- Interactions:
 - Potent CYP3A4 inducers can decrease serum everolimus levels. If concomitant administration of a potent CYP3A4 inducer is required, this may warrant an increase in the dose of everolimus. The use of concomitant moderate CYP3A4 inducers requires close monitoring of everolimus but no dose modifications [132]. Please refer to Appendix 3 for a complete list of potent and moderate inducers of CYP3A4.
 - Potent CYP3A4 and/or P-glycoprotein inhibitors can increase serum everolimus levels and should not be given concurrently. Moderate inhibitors can produce mild-moderate increases in serum levels and may warrant a dose reduction in everolimus [132]. Please refer to Appendix 4 for a complete list of potent and moderate inhibitors of CYP3A4.
- Patients on everolimus should not be immunized with any live vaccines within 7 days of starting study therapy. They should also avoid close contact with individuals who have received attenuated live vaccines. Examples of live vaccines include intranasal influenza, measles, mumps, rubella, oral polio, BCG, yellow fever, varicella and TY21a typhoid vaccines.

5.3 Letrozole

- Definition: Letrozole is a type II (competitive) non-steroidal aromatase inhibitor.
- Mechanism of action: Letrozole binds the heme group of aromatase, blocking the conversion of androstenedione and testosterone to estrone and estradiol, respectively [94].
- Pharmacokinetics/dynamics: Letrozole has a half life of 2-4 days [133,134]. It strongly inhibits CYP2A6 and weakly inhibits CYP2C19. It is a minor substrate of CYP3A4 and CYP2A6, and is converted by hepatic metabolism into an inactive carbinol metabolite [135].
- The dose of letrozole in this study of 2.5mg po daily is the one used in for pediatric patients >25kg [68,136]. The weight range for a 12 years old being 30kg-60kg (5%-95%), it is expected that all pediatric patients would fall into that range.
- Supply: Letrozole is manufactured by Novartis Pharmaceuticals as a 2.5 mg oral tablet. Letrozole is supplied by Novartis for this study.

- Storage: Letrozole should be stored at an ambient temperature of 25 °C (77 °F) with brief temperature excursions ranging from 15 °C-30 °C (59 °F-86 °F) permitted. The drug should be stored in its original packaging, and exposure to light and moisture should be avoided [137].
- Administration: Letrozole is administered once daily at the standard dose of 2.5 mg/day.

5.4 Leuprolide

- Definition: Leuprolide is a synthetic nonapeptide GnRH analog with the chemical name 5-oxo-L-prolyl-L-histidyl-L-tryptophyl-L-seryl-L-tyrosyl-D-leucyl-L-leucyl-L-arginylN-ethyl-L-prolinamide acetate. Leuprolide entrapped in polylactic acid polymer microspheres forms a biodegradable depot injection that is hydrolyzed by the body, allowing for sustained release over time [138-140].
- Mechanism of action: Leuprolide binds to GnRH receptors on the pituitary gland, causing an initial surge in gonadotropin and gonadal steroid hormone release. This is followed by GnRH receptor downregulation, and subsequent inhibition of pituitary-gonadal function in both men and women that is reversible. The gonadotropin surge or “flare” occurs within the first week following administration of the GnRH agonist and chemical castration achieved by the fourth week [38-41,141].
- Pharmacokinetics/dynamics: Leuprolide is available as a monthly depot injection of 7.5 mg monthly. This formulation is the one recommended for premenopausal ovarian suppression and in prostate cancer [142, 143]. After injection of 3-monthly leuprolide, peak plasma concentration is reached at approximately 3 hours after which steady state concentrations are achieved by Day 7, persisting until the next injection [141,144]. Excretion is primarily renal. No pharmacokinetic studies of leuprolide have been conducted in patients with hepatic or renal dysfunction.
- Supply: Leuprolide is manufactured by Takeda Pharmaceuticals for Abbott Pharmaceuticals. Leuprolide is supplied by Abbott for this study.
- Storage: Leuprolide should be stored at an ambient temperature of 25 °C (77 °F). Brief temperature excursions ranging from 15 °C-30 °C (59 °F-86 °F) are permitted. The drug should be stored in its original packaging, and exposure to light and moisture should be avoided [145].
- Administration: Leuprolide depot 7.5 mg will be administered intramuscularly monthly (+/- 7 days). This is the same dose used in premenopausal breast cancer patients. This is also the recommended dose for pediatric patients >25 kg [146]. Given that the weight range for a 12 years old being 30kg-60kg (5%-95%), it is expected that all pediatric patients would fall into that range.

6.1 CRITERIA FOR SUBJECT ELIGIBILITY

6.2 Subject Inclusion Criteria

- Patients \geq 12 years old.

MEMORIAL SLOAN-KETTERING CANCER CENTER
IRB PROTOCOL

IRB#: 11-211 A(6)

- Pathologically confirmed diagnosis of advanced and/or unresectable FLL-HCC. This will be performed by the participating centers on submitted specimens. If the submitted material is insufficient for analysis, a repeat biopsy is recommended.
- ECOG performance status 0-2 (see Appendix 1); Lansky performance score of $\geq 60\%$ for patients 12-16 years old (see Appendix 2)
- Adequate hematologic, renal and hepatic function defined as:
 - Hematologic: ANC $\geq 1.0 \times 10^9/L$, platelets $\geq 50 \times 10^9/L$.
 - Renal: creatinine $\leq 2 \times$ upper limit of normal, or creatinine Clearance of $\geq 60 \text{ cc/mL}/1.73 \text{ m}^2$ for patients > 16 years old. For patients ≤ 16 years of age, creatinine Clearance of $\geq 70 \text{ cc/mL}/1.73 \text{ m}^2$ or serum creatinine based on the following chart:

Creatinine clearance or radioisotope GFR $\geq 70 \text{ ml/min}/1.73 \text{ m}^2$ or serum creatinine based on age/gender as follows:

Age	Maximum Serum Creatinine (mg/dL)	
	Male	Female
10 to < 13 years	1.2	1.2
13 to < 16 years	1.5	1.4
≥ 16 years	1.7	1.4

The threshold creatinine values in this Table were derived from the Schwartz formula for estimating GFR (Schwartz et al. J. Peds, 106:522, 1985) utilizing child length and stature data published by the CDC.

- Hepatic: total bilirubin $\leq 2 \text{ mg/dL}$, alanine and aminotransferase levels $\leq 5 \times$ upper limit of normal for age.
- Fasting blood glucose $< 1.5 \times$ upper limit of normal . If fasting glucose $\geq 1.5 \times$ upper limit of normal, adequate glycemic control (fasting glucose $< 1.5 \times$ upper limit of normal) for three weeks is recommended before starting protocol therapy.
- At least 1 target lesion measurable by Response Evaluation Criteria in Solid Tumors (RECIST 1.1) guidelines.
 - Target lesion(s) must not lie within a previously resected, irradiated, ablated, or chemoembolized area. If a lesion does lie in such an area, there must be evidence of a $\geq 20\%$ increase in diameter and/or the appearance of a new lesion on subsequent imaging in order for such a lesion to be considered a target lesion.
- Prior systemic therapy is allowed. Prior surgery, locoregional ablative or embolic therapies are also permitted provided that the criteria for measurable disease as outlined above are met.
- Concurrent antiviral therapy for hepatitis B is permitted.

- Women of childbearing potential must be practicing an effective method of birth control that may include intrauterine devices (both hormonal and non-hormonal are acceptable), double-barrier method, male partner sterilization or abstinence, before enrollment, and throughout the study and for 6 months after receiving the last dose of study drug. Men must agree to use a double barrier method of birth control and to not donate sperm during the study and for 6 months after receiving the last dose of study drugs. Sperm banking is acceptable for interested male patients enrolled on study prior to initiating treatment. Prescription oral contraceptives, contraceptive injections, and contraceptive patch are not approved methods of contraception and are not allowed in this study.
- Negative pregnancy test (serum hCG) result (applicable to women of child bearing potential) within 7 days before Cycle 1 Day 1 of study treatment.

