1.0 PROTOCOL SUMMARY AND/OR SCHEMA

Fibrolamellar hepatocellular carcinoma (FLL-HCC) is a rare primary liver malignancy affecting adolescents and young adults without an underlying history of chronic liver disease. While surgical resection offers the possibility of long-term disease control and prolonged survival, there are no effective systemic therapies for patients with unresectable disease, for whom median survival is 12 months or less. The paucity of patients with this disease has also made it extremely challenging to conduct clinical trials dedicated to FLL-HCC. As such, patients with FLL-HCC that cannot be resected represent an orphan population in need of novel, effective therapies.

The pathogenesis of FLL-HCC is largely unknown, though several potential drivers have been identified. FLL-HCC tumor overexpression of aromatase, in association with a hyperestrogenic clinical phenotype, as well as the PI3K/Akt/mTOR pathway have been reported by both immunohistochemistry and gene expression profiling. Based on the known interactions between estrogen and the PI3K/Akt/mTOR pathway in breast cancer, we hypothesize that suppression of central and peripheral estrogen production and mTOR inhibition will have antineoplastic activity in FLL-HCC. These hypotheses are the basis of the proposed clinical trial entitled: “A Randomized Three Arm Phase II Study of (1) Everolimus, (2) Estrogen Deprivation Therapy (EDT) with Leuprolide + Letrozole and (3) Everolimus + EDT in Patients with Unresectable Fibrolamellar Hepatocellular Carcinoma (FLL-HCC).”

This will be a 2-part protocol in which patients are initially randomized, in Part 1, to one of the three treatment arms shown in Figure 1 below. Upon disease progression, patients receiving everolimus alone, or EDT alone, may be treated with combined everolimus and EDT during Part 2 of the study as part of an exploratory analysis. The primary study endpoint is progression-free survival at 6 months (PFS6).

Figure 1: Protocol schema

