2.1 OBJECTIVES AND SCIENTIFIC AIMS

2.2 Primary efficacy endpoint (Arm A: everolimus vs. Arm B: estrogen deprivation therapy (EDT) with leuprolide + letrozole vs. Arm C: everolimus + EDT) of the study:

- Progression-free survival at 6 months (PFS6)

2.3 Secondary objectives:

- To evaluate median progression-free survival
- To evaluate median overall survival
- To evaluate objective response rate by RECIST 1.1 guidelines
- To evaluate rate of conversion to resectable status
- To evaluate safety/toxicity profiles.
- To evaluate correlative tissue and serum biomarkers.

2.4 Exploratory analysis for Part 2 (combined everolimus + EDT) of the study:

- PFS, measured as the time from the start of the combination therapy till progression, clinical progression or death, whichever occurs first, will be evaluated in patients who switch from either Arm A or B to combination therapy.

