3.3 Prognosis of patients with FLL-HCC

Historically, FLL-HCC has been perceived as the more indolent counterpart of typical HCC, but patients with metastatic, unresectable disease face a grim prognosis. While patients with resected disease can do extremely well, with 5-year and median survival outcomes of up to 76% and 112 months, respectively, those with unresectable disease fare much worse, surviving only 12-14 months [11-13]. The presence of lymph node metastases has also been significantly associated with shorter recurrence-free and overall survival times [4,11]. Growing evidence suggests that patients with FLL-HCC appear to have a prognosis similar to that of patients with typical HCC without cirrhosis [4,21,22], suggesting that absence of cirrhosis and not an intrinsically less aggressive disease biology, may drive the natural history of FLL-HCC [4]. A pediatric series found no significant differences in 5-year event-free and overall survival between 36 typical HCC and 10 FLL-HCC patients of all stages who were randomized to two different cisplatin-based chemotherapy regimens following surgery or biopsy [21]. Approximately 80% of all patients had advanced and/or unresectable disease, and survival was uniformly poor regardless of histologic subtype (13.6 months for FLL-HCC vs. 3.3 months for typical HCC, $p = 0.16$). The estimated progression-free survival at 6 months in FLL-HCC and typical HCC patients were 50% and 30%, respectively [21]. Of note, these values were derived from a treatment-naïve patient population and it is anticipated that the PFS6 for a heavily pretreated FLL-HCC would be lower at approximately 40%.

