3.4 Therapy for FLL-HCC

Surgical resection is the mainstay of definitive therapy for patients with FLL-HCC, providing the opportunity for cure as well as prolonged survival. Unfortunately, the majority of patients relapse within 6-33 months [11,20,23]; in one series, the 5-year recurrence-free survival rate was only 18% [14]. The current management paradigm in this disease is an aggressive surgical approach with repeated resections of recurrent disease. When hepatectomy is contraindicated, liver transplantation may be an option although clinical experience with this approach is limited [5,24]. Among non-surgical candidates, doxorubicin-based hepatic artery chemoembolization has shown activity [25,26]. Once disease becomes so widespread that surgery and locoregional ablative therapies are no longer possible, systemic therapies are the only alternative.

Clinical experience with cytotoxic chemotherapy has not demonstrated substantial activity in FLL-HCC. Attempts to decrease the risk of post-operative relapses with adjuvant cisplatin, 5-fluorouracil or doxorubicin containing chemotherapy have been ineffective [5,23]. Chemotherapy in advanced FLL-HCC has also not shown any evidence of clinically meaningful activity [21]. The only notable exception is the combination of 5-fluorouracil and IFN α 2b which produced a 75% objective response rate, including one complete response, and a median survival of 23.1 months among 9 FLL-HCC patients in a phase II study that also included 34 patients with typical HCC [27]. These studies,

although limited by small sample sizes and highly heterogeneous study populations, underscore the need for better systemic therapies for patients with advanced, unresectable FLL-HCC.

[figure not shown]

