 - Objective response rate by RECIST 1.1 guidelines
 - Rate of conversion to resectable status
 - Safety and toxicity
 - Correlative serum and tissue biomarker studies.
- Kaplan-Meier PFS will be measured from the date that study therapy is initiated until the date of

first evidence of radiographic disease progression, global clinical deterioration as determined by study investigators, or death.

- Kaplan-Meier OS will be measured from the date that study therapy was commenced until the date of death.
- Objective responses will be reported using RECIST guidelines (version 1.1). Objective response will be estimated using binomial proportions and exact 95% CIs will be provided.
- Conversion to resectable status to be determined by hepatobiliary surgeons in conjunction with radiological assessment of response to therapy.
- Adverse events/toxicity will be monitored and recorded using the CTCAE version 4.0 and summarized descriptively.
- Baseline serum measurements will be correlated with PFS6 (binary endpoint) using Fisher's exact test for categorical serum measurements and using Wilcoxon rank sum test for continuous measurements. For each time point at which serum measurements are collected, changes in the different binary serum markers from baseline will be correlated with PFS6 using conditional logistic regression to account for the paired nature of the data while Wilcoxon signed-rank test will be used for continuous measurements.
- Associations between baseline tissue biomarkers and PFS6 will be assessed using Fisher's exact test for categorical biomarkers, trend tests for ordinal biomarkers and Wilcoxon rank-sum test for continuous biomarkers. For patients undergoing surgery, changes in tissue biomarkers from baseline to surgery will be summarized descriptively in an exploratory fashion.

Exploratory analysis for Part 2 of protocol (combination therapy).

- PFS will be evaluated for patients who were on Arm A (everolimus) or Arm B (EDT) during Part 1 of the study who subsequently received combined everolimus + EDT during Part 2.
- PFS will be measured as the time from the start of the combination therapy till progression or death whichever comes first.

Biomarker analysis and data interpretation

- Baseline tissue biomarkers will be correlated with PFS6.
- Baseline levels of hormones will be correlated with PFS6.
- Baseline levels of tumor markers will be correlated with PFS6.

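### The inclusion criterion does not require unresectable disease, so patients who cannot convert to resectable status can enter the conversion endpoint

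*Combined protocol and SAP*

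**What the plan says.** The population is described in three places, and they do not agree.

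- The title, given in Section 1.0, names patients with unresectable disease.
- Section 4.2 says that "patients with advanced (recurrent or metastatic), unresectable FLL-HCC will be randomized to one of three arms". Both conditions apply, and the parenthesis says what advanced means.
- Section 6.2, the inclusion list, asks for "Pathologically confirmed diagnosis of advanced and/or unresectable FLL-HCC". Either condition is enough.

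Section 15.1 tells staff to confirm eligibility against the eligibility section and to complete a checklist, so Section 6.2 is the operative text. Section 6.2 also permits prior surgery. Nothing else in Sections 6.2 or 6.3 refers to resectability at entry.

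Section 2.3 lists the secondary objective "To evaluate rate of conversion to resectable status". Section 14.0 adds only who decides: "Conversion to resectable status to be determined by hepatobiliary surgeons in conjunction with radiological assessment of response to therapy". It gives no denominator. The pretreatment evaluations in Sections 8.2 and 8.3 and the calendar in Section 10.0 require baseline imaging but no judgement of resectability.

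**The concern.** Under Section 4.2's own explanation of advanced, a patient with measurable, recurrent disease that a surgeon could remove satisfies Section 6.2. The background shows that such disease exists, since Section 3.4 describes "an aggressive surgical approach with repeated resections of recurrent disease".

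A patient who is resectable at entry cannot convert to resectable. If surgeons later call the disease resectable, the patient may be scored as a conversion that did not happen. If not, the patient sits in the denominator with no possibility of converting. Without a recorded starting state, neither case can be identified afterwards.

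The primary endpoint is also exposed. Each arm's PFS6 is tested against a fixed 40%, so a change in case mix shifts the tested rate whether or not the drugs work, and randomization does not protect that test.

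**Working it through.** **1. The wording.** The title requires unresectable disease. Section 4.2 requires advanced and unresectable. Section 6.2 requires advanced or unresectable or both. The patients admitted by Section 6.2 but by neither of the others are those with recurrent or metastatic, resectable disease. The exclusions in Section 6.3 do not remove them. The pathology review named in Section 6.2 is done on specimens, which cannot show resectability.

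**2. Conversion rate.** Take an arm that reaches 28 patients (Section 14.0). Let k be resectable at entry and let c be the true conversion rate among the other 28 − k. The documents give neither k nor c; k = 3 is an illustration.

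- All k scored as conversions: they contribute k/28 = 3/28 = 10.7 percentage points to the reported rate. The excess over c is (k/28)(1 − c), which is 10.7 points at c = 0 and 9.6 points at c = 0.10.
- None scored as conversions: the reported rate is c(28 − k)/28 = c × 25/28 = 0.893c. A true 10% is reported as 8.9%.

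This step needs no assumption about prognosis.

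**3. The plan's PFS6 design, reproduced.** Inputs from Section 14.0: 16 patients in stage 1, stop at 6 or fewer progression free; 28 in total, promising at 15 or more; null 40%, alternative 64%; both errors 10%; early termination 53%.

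P(promising) = Σ over x = 7 to 16 of P[Bin(16, p) = x] × P[Bin(12, p) ≥ 15 − x]

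- At p = 0.40: 0.0989, with early termination 0.527.
- At p = 0.64: 0.9019.

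The stated figures hold, and requiring unresectability changes none of them.

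**4. PFS6 with resectable entrants.** Let f be their share, q their PFS6, and s the share of those otherwise progression free who leave before the 6-month scan. Section 14.0 counts patients who come off study before that scan as events. All three values are assumptions. With an inactive drug and 40% in the other patients,

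p = (1 − f) × 0.40 + f × q × (1 − s)

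| f | q | s | p | P(promising) |
|---|---|---|---|---|
| 0 | – | – | 0.40 | 0.099 |
| 10% | 0.6 | 0 | 0.42 | 0.142 |
| 10% | 0.8 | 0 | 0.44 | 0.197 |
| 20% | 0.8 | 0 | 0.48 | 0.335 |
| 20% | 0.8 | 50% | 0.40 | 0.099 |
| 20% | 0.8 | 75% | 0.36 | 0.042 |
| 20% | 0.8 | 100% | 0.32 | 0.014 |

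The shift changes sign where q(1 − s) = 0.40, that is at s = 1 − 0.40/q: one third for q = 0.6, one half for q = 0.8, 60% for q = 1.0. In the last row, if the drug works and the other patients have PFS6 of 64%, the arm's rate is 0.8 × 0.64 = 0.512 and power falls from 0.90 to 0.47.

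**The case against.** **Intent is clear.** The title and Section 4.2 both say unresectable, Section 18.1 has the study chair review eligibility, and the checklist is not in the documents, so it may already ask about resectability. Section 3.4 places systemic therapy after surgery and locoregional treatment are no longer possible. All of this stands as evidence of intent, and nothing shows that resectable patients would in fact be enrolled or how many. It does not change the rule that staff are told to apply, and the chair's review names no resectability standard.

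**A baseline can be reconstructed.** Triphasic liver imaging is required within four weeks before treatment, and assessing response implies comparison with it. This stands in part: the scans will exist. The surgical judgement made from them is not required, and the denominator is still unstated.

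**A reader might infer that PFS6 is inflated.** Section 3.3 gives resected patients a median survival of up to 112 months, whereas "those with unresectable disease fare much worse, surviving only 12-14 months". The documents do not support that inference, for three reasons. The 112 months is overall survival after resection, not PFS6 with an unresected recurrence on study drug. Early exits count as events, and the documents do not say whether resection takes a patient off study: Section 13.0 does not list it but does list a treatment delay of more than four weeks, while Section 10.0 foresees surgery on protocol therapy. Finally, the 40% is not an unresectable-only benchmark. Section 3.3 lowers it for heavy pretreatment from 50% in a pediatric series in which about 80% of all patients, both histologies together, had advanced and/or unresectable disease.

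**Conclusion.** Section 6.2 is wrong as written: it conflicts with the title and Section 4.2, and read with Section 4.2's explanation of advanced it admits resectable patients.

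The firm consequence is for the conversion rate. Any patient resectable at entry is either a false conversion or dead weight in the denominator, at 3.6 points each in an arm of 28 (1/28), or 10.7 points for three. How many would enrol is unknown. The endpoint is secondary and has no decision threshold.

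For PFS6 the conclusion is limited to possible bias in either direction, of unknown size. The chance of declaring an inactive arm promising ran from 0.014 to 0.335 in step 4, but only because f, q and s were assumed. The comparison between arms used to pick a winner is less exposed, because randomization should spread such patients across arms.

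**What to change.** 1. Reconcile Section 6.2 with the title and Section 4.2 so that unresectability is required of every patient. Section 4.2's phrase should not simply be copied, because read literally it would exclude newly diagnosed, non-metastatic disease that is unresectable, which the title covers. Possible wording: unresectable FLL-HCC, whether locally advanced, recurrent or metastatic.
2. Record on the existing eligibility checklist that the disease was judged unresectable at entry, from the baseline imaging already required.
3. State in Section 14.0 that the conversion rate is computed only in patients so recorded.

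The cost is one reworded criterion, one checklist field, one sentence in the analysis section and the loss of a few resectable candidates from accrual. The sample size, error rates and early-termination probability are unchanged.
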